2.14.6 Stopping Rules (Study Level)

The following criteria result in an immediate stop of dosing and will result in a temporary halt of the study:

Any relevant information, from this trial or from outside of this trial, indicating a relevant deterioration of the benefit-risk ratio. In particular, consistently observed serious adverse events (SAEs) or severe drug-related AEs will be thoroughly assessed by the medical monitor and Study Steering Committee.

Resuming the trial after a temporary halt requires an approved substantial amendment. For discontinuation of study intervention for individual study participants, see [Section 2.14.10](#).

2.14.7 *Continued Access to Study Intervention After the End of the Study*

No treatment with study medication will be provided after the end of the planned 24-week treatment period or after early withdrawal of treatment.

2.14.8 *Concomitant and Prohibited Therapy in the Study Eye*

No other ocular topical drugs (eye drops) should be taken during the study unless prescribed by the treating study physician and after discussion with the sponsor and medical monitor. If topical therapy (eye drops) is prescribed, the application of such therapy should not occur within 10 minutes (before or after) of instillation of study therapy. Other approved or investigational therapies for retinal disease (ie, oral, topical, and/or intravitreal injected drugs like steroids or anti-VEGFs) are not permitted, unless applied as rescue therapy (Section 2.14.9). Such intake is to be recorded (see below). Contact lens wear is strictly prohibited from the time of screening throughout the study. If participant has current contact lens use at screening, contact lens use should be discontinued immediately, and a 14 day ocular surface stabilization period is needed between screening and baseline.

Concomitant medications are to be recorded in the eCRF.

The medical monitor should be contacted if there are any questions regarding concomitant or prior therapy.

2.14.9 *Rescue Therapy*

Participants meeting any of the following criteria would qualify for rescue with anti-VEGF therapy and/or PRP laser after consultation with the medical monitor:

Objective Rescue Therapy Criteria:

- Worsening DRSS level to 65 or higher as confirmed by the central reading center
- Development of ASNV
- Decrease in BCVA of ≥ 10 ETDRS letters from BL associated with presence of new fluid or an increase in fluid in the central subfield compared to baseline at any visit

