2.14.10.1 Permanent Discontinuation

In rare instances, it may be necessary for a participant to permanently discontinue (definitive discontinuation) study intervention. If study intervention is permanently discontinued, the participant may remain in the study for continued assessment of safety and efficacy outcomes.

Unscheduled visits may be performed as deemed appropriate by the investigator, in particular, in case of withdrawal due to an AE.

Participants *must* be withdrawn from the *study intervention* for any of the following reasons:

- If rescue therapy has been initiated
- Safety concerns for a participant by the investigator or the sponsor
- Vision threatening complication meeting rescue criteria and/or progression to worse than mild PDR with DRSS > 61
- Pregnancy (see [Section 2.17.4](#) for details)

Necessity to withdraw the participant from the study will be assessed case-by-case by the investigator in consultation with the medical monitor.

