2.16.2 Color Fundus Photography (CFP)

The anatomical state of the retinal vasculature will be evaluated by an ophthalmologist from posterior segment examination and CFP. All digital CFP images need to be taken by a certified technician following an acquisition protocol for modified 7-field stereoscopic color fundus photographs or 4-wide field imaging of the central reading center at the visits indicated in the SoA ([Section 2.15.1](#)).

All CFPs will be transmitted to the central reading center for ETDRS DRSS (see [Appendix 2](#)) grading and storage. The images from the screening visit of both eyes will be used as part of the eligibility assessment regarding the severity of diabetic retinopathy.

CFPs may, in addition, be evaluated for additional, exploratory, endpoints. This may include assessment of microaneurysm turnover ([Nunes 2009](#)) or measurement of diameters of retinal vessels as described previously ([Lundberg 2013](#)). This may involve transmission of CFP to additional central reading centers.

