- replaced by multiple imputation algorithm based on data from participants not affected by the respective ICE when applying hypothetical strategy
- kept in the analysis when applying treatment policy strategy

Comparison of the primary endpoint will be made between each dose group and the combined vehicle control group using a Mantel-Haenszel (MH) test of the difference in 2 proportions stratified by the randomization stratification factor (BL DRSS score 47 or 53 or 61B). The estimated MH risk difference will be summarized along with the 2-sided 90% CI using MH stratum weights and the Sato variance estimator. The primary efficacy analysis will be performed on the ITT Analysis Set, while the PP set will be used as supplementary analyses. ICEs and missing data will be handled as described above.

The primary efficacy analysis will also be performed by demographic subgroups including age, gender, and race to assess the consistency of the treatment effect. Additional subgroup analyses may also be conducted and will be described in the Statistical Analysis Plan (SAP).

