**3.2.2 Primary Efficacy Endpoint and Estimand**

The primary efficacy outcome measure of the study will be the proportion of participants who have improved by  $\geq 2$  steps from baseline at Week 24 as determined by central reading center assessment using the DRSS. The primary clinical question of interest is to determine the effectiveness of different doses of OCT166 versus vehicle control on  $\geq 2$  steps improvement from BL in DRSS score at Week 24 without requiring rescue treatment if the study drug is not discontinued prior to Week 24. This will support the dose selection for subsequent pivotal studies of OTT166. The estimand for the primary efficacy analysis is defined as follows:

|   | Primary Estimand  |
|---|--|
| Treatment conditions of interest | OTT166 5 mg/day, OTT166 10 mg/day and matching vehicle control   |
| Participant Population           | DR participants with Type 1 or Type 2 diabetes under adequate control (HbA1c $\leq 12.0\%$ ) who show typical fundus alterations and have been diagnosed with moderately severe to severe NPDR or mild PDR as defined by the DRSS Steps 47, 53, and 61B, with BCVA $\geq 69$ ETDRS letters, CST of $\leq 325 \mu\text{m}$ , and a normal foveal contour. |
| Endpoint                         | $\geq 2$ steps improvement from BL in DRSS score at Week 24  |
| Population level summary         | Difference in proportion of participants achieving $\geq 2$ steps improvement from BL in DRSS score at Week 24 between each OTT166 treatment group and the combined vehicle control group.   |

|   | Primary Estimand  |
|---|--|
| Intercurrent events (ICEs) and strategies to handle ICEs | 
a) Rescue treatment in the study eye due to worsening DRSS level to 65 or higher prior to assessment of DRSS at Week 24
Composite strategy (non-response)
 
b) Death prior to DRSS assessment at Week 24
Hypothetical strategy
 
c) Use of rescue treatment in the study eye for any other reason prior to DRSS assessment at Week 24
Composite strategy (non-response)
 
d) Premature discontinuation of study drug for any reason prior to DRSS assessment at Week 24
Hypothetical strategy
 
e) Study drug compliance <75% through Week 24
Treatment policy strategy
 
f) Study drug compliance between 75% to <90% through Week 24
Treatment policy strategy
 |

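### An eye taken off study drug for DRSS 65 or higher, not rescued and still followed has its observed Week 24 grade replaced by draws from a model holding only arm and stratum

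*SAP*

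**What the plan says.** Protocol 2.14.10.1 lists the reasons for which study drug must be stopped. Starting rescue is one item; "Vision threatening complication meeting rescue criteria and/or progression to worse than mild PDR with DRSS > 61" is another. In the scale in Protocol Appendix 2 the level after 61 is 65, so this threshold and the DRSS 65 rescue criterion are the same. After stopping, "the participant may remain in the study for continued assessment of safety and efficacy outcomes".

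Protocol 2.14.9 names "Worsening DRSS level to 65 or higher as confirmed by the central reading center" as an objective rescue criterion. Eyes that meet a criterion "would qualify for rescue with anti-VEGF therapy and/or PRP laser after consultation with the medical monitor". Rescue is therefore possible but not automatic. Protocol 2.20.2 also times meeting the criteria and receiving rescue as two separate endpoints.

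SAP 3.2.2 and the matching table in Protocol 2.21.2.1 define the intercurrent events (ICEs):

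- ICE a, composite (non-response): "Rescue treatment in the study eye due to worsening DRSS level to 65 or higher prior to assessment of DRSS at Week 24".
- ICE c, composite (non-response): rescue of the study eye for any other reason.
- ICE d, hypothetical: "Premature discontinuation of study drug for any reason prior to DRSS assessment at Week 24".

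Composite events outrank the others, which helps only if a composite event occurred. Under the hypothetical strategy, a Week 24 result observed after the event is "replaced by multiple imputation algorithm based on data from participants not affected by the respective ICE when applying hypothetical strategy" (Protocol 2.21.2.1, repeated in SAP 4.10.1.2). The SAP model regresses DRSS level on randomized arm and randomization stratum and derives response from the imputed level, with 100 imputations.

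Interim grades will exist. The study eye is photographed at every visit, and Protocol 2.16.2 says "All CFPs will be transmitted to the central reading center for ETDRS DRSS" grading.

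**The concern.** Both composite events need rescue to have been given. The withdrawal rule does not. Between them sits an eye that reached DRSS 65 or higher, was taken off drug for that reason, was not rescued and was still followed. Its failure has been graded, yet the plan sets the Week 24 grade aside and draws another.

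The draw assumes missing at random given arm and stratum. For these eyes that is not tenable: withdrawal was triggered by interim DRSS grades, which the model omits. The draw treats the eye as typical of participants who stayed on drug in the same arm and stratum, so a share of draws makes it a responder. The primary analysis can then score the same progression in two ways, depending only on whether rescue was administered.

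A second point is conditional. For secondary proportions, SAP 4.10.1.2 takes over the primary approach, with a parenthesis that names ICE handling as well as missing data. If that is applied literally, an observed event in the proportion developing DRSS 65 or above can be overwritten, while the time-to-event analysis of the same endpoint counts it.

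**Working it through.** **Which eyes are affected**

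| Study eye | Event met | Week 24 value used |
|---|---|---|
| DRSS ≥65 before Week 24, rescued | a and d; a has priority | non-response |
| DRSS ≥65 before Week 24, drug stopped, not rescued, followed | d only | observed grade dropped, imputed |
| DRSS ≥65 reached, still on drug | none of a, c, d | observed grade |
| DRSS ≥65 first seen at Week 24 | none of a, c, d | observed non-response |

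Only the second row is a problem.

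**The plan's own figure (SAP 4.13).** For 0.26 vs 0.06, one-sided alpha 0.05 and 90% power, the continuity-corrected chi-square formula gives 66 per group (56 uncorrected), as stated. Allowing 5% attrition gives 70. The sample size is sound.

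**Inputs.** Rates 0.26 and 0.06 and 70 per arm come from SAP 4.13. The documents give neither the share P of an arm progressing before Week 24 nor the share r of those rescued; both are assumed. The reference counts every progressor as a non-responder.

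SE = sqrt(0.26×0.74/70 + 0.06×0.94/70) = 0.0596.

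**Donor-rate calculation.** Donors are the participants still on drug. If each unrescued progressor responds at its donors' rate p/(1−P), the analysed rate in an arm is p[1 + P(1−r)/(1−P)]. With P = 10% and r = 0.5 the factor is 1 + 0.05/0.90 = 1.0556, so the rates are 0.2744 and 0.0633 and the difference is 0.2111 instead of 0.2000.

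**Simulating the planned model.** Normal regression of the Week 24 step on arm and stratum, MH risk difference, 70 per arm, 1,500 trials, 30 imputations each. Assumed: one level per step (47, 53, 61B, 65 coded 5 to 8), baseline mix 50/35/15%, progression weighted to 53 and 61B, and changes from −3 to +1 steps giving a true difference of about 0.20. The SAP does not say whether imputed levels are rounded, so both are shown.

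Excess in the primary difference, P = 10% in each arm:

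| Rescued | Donor rate | Unrounded | Rounded |
|---|---|---|---|
| 0% | 0.0222 | 0.0092 | 0.0164 |
| 50% | 0.0111 | 0.0044 | 0.0079 |
| 80% | 0.0044 | 0.0019 | 0.0034 |
| 100% | 0 | 0 | 0 |

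A separate simulation with its own assumed distributions drew unrescued progressors as responders in about 10% (active) and 3% (vehicle) of imputations unrounded, and 23% and 9% rounded. By hand, the excess at r = 0.5 is then 0.05×(0.10−0.03) = 0.0035 and 0.05×(0.23−0.09) = 0.0070, close to the table. Per 70 active eyes, 3.5 are unrescued progressors. Expected false responders are 3.5×0.10 = 0.35, 3.5×0.23 = 0.8, or 3.5×0.26/0.90 = 1.0 at the donor rate.

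**Direction.** The error changes sign when the vehicle share of such eyes exceeds the active share by more than the ratio of their draw rates, roughly 3 to 4. At 2% active and 10% vehicle with none rescued, the simulated excess is −0.0014 unrounded and −0.0047 rounded.

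**Conditional secondary, illustration only.** Let w be the share first reaching DRSS 65 at Week 24, and count rescued eyes as events. The true proportion is P + w; the analysed one is Pr + w + P(1−r)w/(1−P). With w = 1%, P = 2% active and 10% vehicle, the truth is 3.00% vs 11.00%. At r = 0.5 the analysed values are 2.01% vs 6.06%, so 8.0 points become 4.05. At r = 0.8 they are 2.60% vs 9.02% (6.42 points); at r = 1 nothing changes.

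**The case against.** **The estimand is deliberate.** SAP 3.2.2 asks about response if study drug is not discontinued. That stands, and the hypothetical strategy as such is not the fault. But the same sentence asks for response without requiring rescue, and here discontinuation is the consequence of an outcome grade already seen on drug. ICE a scores that same progression as failure.

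**The set may be nearly empty.** DRSS 65 is itself a rescue criterion, so most such eyes may be rescued. This stands as a limit on size: nothing in the documents shows that the set is empty, and nothing gives a count.

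**Other analyses keep the observed grades.** This is true of the observed-case and LOCF sensitivity analyses, the supplementary time to two-step improvement, and the time-to-event secondaries. They can expose a discrepancy but do not alter the primary result. The supplemental estimand changes only ICEs c and e. The data review meeting in SAP 4.4.1 confirms ICEs as defined and has no rule for moving an eye out of ICE d.

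**Pre-event grades may already be used.** The SAP's Amendment 1 log mentions data up to the event. That describes superseded text; the current section has no such term.

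**Adding interim grades would suffice.** In simulation it brings the share drawn as responders below 0.1%, but by extrapolation: withdrawal leaves almost no on-drug donors at DRSS 65 or higher.

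**Stronger readings the documents do not support.** A reader might infer that any unrescued progression escapes non-response; eyes still on drug and progression first seen at Week 24 keep their observed grades. A reader might infer a material bias in favour of OTT166; the shift is small and can go either way. A reader might infer that the DRSS 65 secondary contrast disappears; that needs almost no rescue, unsourced progression rates, and a broad reading of a sentence whose subject is missing data.

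**Conclusion.** The gap is real, narrow and worth closing before database lock. It follows from the current text. Its size does not, because the number of affected eyes is unknown. At an assumed 10% progressing per arm with half rescued, the bias is about 0.07 to 0.13 standard errors (0.0044/0.0596 and 0.0079/0.0596), and 0.19 at the donor rate (0.0111/0.0596). That is unlikely to decide the trial. The stronger reasons to act are that an eye with a confirmed failing grade can be counted as improved, and that identical progression is scored differently according to whether rescue was given. The figures rest on assumed step coding, baseline mix and step-change distributions, and on progressors being non-responders at Week 24. The secondary point holds only if the sponsor applies the ICE-handling parenthesis as in the primary analysis; its size depends wholly on assumed progression and rescue rates.

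**What to change.** 1. **SAP 3.2.2.** Add an ICE: discontinuation of study drug because of reading-center-confirmed DRSS 65 or higher in the study eye before Week 24, whether or not rescue was given; composite strategy (non-response). Limit ICE d to discontinuation for any other reason. This wording leaves eyes that were never withdrawn untouched. Unrescued withdrawals for ASNV or macular fluid stay under ICE d, because those findings are not DRSS grades and do not settle this endpoint.
2. **SAP 4.10.1.2, primary.** For the remaining ICE d and missing cases, add the study-eye DRSS grades collected before the event to the imputation model, and state whether imputed levels are rounded before response is derived.
3. **SAP 4.10.1.2, secondary proportions.** State that an observed DRSS 65-and-above event is kept as an event and not re-imputed.

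No clinical rule changes; the withdrawal and rescue passages must be reconciled with the ICE list. The cost is SAP wording and programming, with no new data. SAP 4.14 gives the SAP precedence over the protocol's planned analyses and allows changes up to database lock, so the table in Protocol 2.21.2.1 can be aligned at the next amendment. The downside is a possibly slightly smaller primary estimate.

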### 3.2.3 Secondary Endpoints

The secondary outcome measures are as follows:

- Proportion of participants developing worse than mild PDR (DRSS 65 and above) at Week 24.
- Proportion of participants who develop ASNV determined by the investigator at Week 24.
- Time to development of PDR worse than mild (DRSS 65 and above).
- Proportion of participants who develop CI-DME at Week 24.
  - CI-DME is defined as the presence of fluid in the central subfield in participants who have no fluid at baseline or CST > 325 μm.
- Time to development of CI-DME.
- Proportion of participants with change in DRSS steps at Week 24 compared to baseline.
  - Change in DRSS steps is defined as DR worsening or improving by 1, 2, or ≥3 steps.

- Proportion of participants with mild PDR (DRSS score 61B) at baseline who regress to NPDR (DRSS score  $\leq 53$ ) by Week 24.
- Mean and median change in BCVA (ETDRS letters) from baseline to Week 24.
- Lines gained/lost in BCVA ( $\pm 5, 10, \text{ and } 15$  ETDRS letters) at Week 24.
- Mean and median change in Area Under the Curve (AUC) for change in BCVA from baseline to Week 24.
  - AUC from baseline to 24 weeks will be calculated by the linear trapezoidal method:

$$AUC_{(t_i - t_{i-1})} = (t_i - t_{i-1}) * \frac{f(t_i) + f(t_{i-1})}{2}$$

$$AUC_{(24-0)} = \sum_{t_0=0}^{24} AUC_{(t_i - t_{i-1})}$$

where,  $t_i = \#$  of weeks since baseline, which may include 0, 4, 8, 12, 16, 20, 24 according to schedule of visits, if available.

- Mean and median change in CST from baseline to Week 24.
- AUC for change in CST from baseline to Week 24.
- Proportion of participants who met the objective rescue criteria as defined in protocol section 2.14.9.
- Time to meet the objective rescue therapy criteria as defined in protocol section 2.14.9.
- Proportion of participants who develop VTC at Week 24
- Time to development of PDR worse than mild (DRSS 65 and above) or CI-DME

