#### *Change from baseline secondary endpoints:*

Handling of missing data of change from baseline in participants without ICES:

- Multiple imputation of the value at Week 24 (for BCVA and CST) assuming missing at random (MAR).

Handling of missing data of change from baseline after ICES:

- Single imputation using the worst value at each visit observed among all participants when applying composite variable strategy.
- Multiple imputation assuming MAR when applying treatment policy or hypothetical strategy.

Handling of data observed after ICES:

- The value will be replaced by a single imputation using the observed worst value at each visit among all participants when applying composite variable strategy.
- Replaced by MAR multiple imputation algorithm based on the assumption that the intercurrent event would not have occurred when applying hypothetical strategy.
- Kept in the analysis when applying treatment policy strategy.

MAR imputation for the continuous secondary endpoints (BCVA and CST) will be generated based on a linear regression model adjusting for treatment group, the randomization strata, and BL score of the analyzed variable where applicable and then the change from baseline will be calculated. A total of 100 imputations will be used followed by the MIANALYZE procedure to combine the estimates.

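### The AUC for BCVA and CST change is summed over whichever visits exist, and the SAP does not carry imputed values into the sum, so an unrescued early leaver's AUC shrinks with the time missed

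*SAP*

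**What the plan says.** SAP 3.2.3 lists two AUC endpoints: "Mean and median change in Area Under the Curve (AUC) for change in BCVA from baseline to Week 24" and "AUC for change in CST from baseline to Week 24". Under the BCVA endpoint it says "AUC from baseline to 24 weeks will be calculated by the linear trapezoidal method". The total is labelled as running from 0 to 24 weeks, but the time points are the number "of weeks since baseline, which may include 0, 4, 8, 12, 16, 20, 24 according to schedule of visits, if available". There is no division by weeks covered, f(t) is not defined, and the CST endpoint has no formula.

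Missing data for change-from-baseline endpoints are covered in SAP 4.10.1.2:

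- Participants without an intercurrent event: "Multiple imputation of the value at Week 24 (for BCVA and CST) assuming missing at random (MAR".
- Data missing after an event handled by the composite strategy, which in SAP 3.2.2 is rescue in the study eye: "Single imputation using the worst value at each visit observed among all participants when applying composite variable strategy". Values observed after such an event are replaced in the same way.
- Data missing after other events, including premature discontinuation of study drug: "Multiple imputation assuming MAR when applying treatment policy or hypothetical strategy". No visit is named.
- The model: "MAR imputation for the continuous secondary endpoints (BCVA and CST) will be generated based on a linear regression model", with treatment group, strata and baseline value as predictors.

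None of these rules mentions the AUC. Protocol 2.21.2.2 leaves secondary estimands and imputation details to the SAP, so no rule elsewhere fills the gap.

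**The concern.** A sum over the available visits covers 24 weeks for a completer and fewer for a participant who leaves. The two are then averaged as if they were the same quantity. With f(t) as change from baseline, every missing interval at the end adds nothing, which is the same as assuming no change over that time. Losses and gains are both understated.

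The rules also treat the two kinds of incomplete participant in opposite ways. The composite rule works visit by visit and moves rescued participants away from zero. For everyone else, the only visit named is Week 24, and nothing links that value to the AUC. What is at stake is the meaning of two secondary endpoints and, if dropout differs by arm, the comparison between arms.

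**Working it through.** **Inputs.** The trapezoid rule and the visits at Weeks 0, 4, 8, 12, 16, 20 and 24 come from SAP 3.2.3. Attrition of about 5% comes from SAP 4.13, where 70 per group less 5% is 70 × 0.95 = 66.5, in line with the stated 66. The plan gives no AUC figure and no expected trajectory, so the courses below are assumed. f(t) is taken as change from baseline, so f(0) = 0.

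**One participant, no imputed value used.** For a change c reached at Week 4 and held, the first interval gives 4 × (0 + c)/2 = 2c and each later one 4c. With last visit at Week L the sum is (L − 2)c, against 22c for a completer. For a linear change, the share of the completer's value is (L/24)².

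| Last visit | Sustained: (L − 2)/22 | Linear: (L/24)² |
|---|---|---|
| Week 4 | 9.1% | 2.8% |
| Week 8 | 27.3% | 11.1% |
| Week 12 | 45.5% | 25.0% |
| Week 16 | 63.6% | 44.4% |
| Week 20 | 81.8% | 69.4% |

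Example: a loss of 12 letters at Weeks 4 and 8 followed by exit scores 6 × (−12) = −72 letter-weeks. A completer with a sustained loss of only 3 letters scores 22 × (−3) = −66.

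**Contrast with rescue.** Take losses of 5 and 10 letters at Weeks 4 and 8. If the participant leaves unrescued, the sum is −10 − 30 = −40. If the participant is instead rescued after Week 8 and the worst value is an assumed loss of 15 letters at Weeks 12 to 24, the sum is −10 − 30 − 50 − 3 × 60 = −270.

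**Group mean.** With dropout d and share s from the table, the fraction retained is 1 − d + d·s. For the sustained course:

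- d = 5%: 95.5% if all leave after Week 4, and 99.1% if all leave after Week 20.
- d = 20% (assumed): 81.8% and 96.4%.

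**Between arms.** Assume dropout of 5% and 15% and the same sustained 6-letter loss in both arms. A completer scores −132. A leaver scores −12 (after Week 4) or −60 (after Week 12). The spurious difference is (0.15 − 0.05) × 120 = 12, or 0.10 × 72 = 7.2 letter-weeks. With a loss, it favours the arm with more dropout. With equal dropout and timing it is zero.

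**Possible corrections.**

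- Dividing by weeks observed, sustained 5 letters: exit after Week 4 gives 10/4 = 2.5, against 110/24 = 4.6 for a completer. On a linear decline to −12 letters it gives −4/4 = −1.0, against −144/24 = −6.0. The bias remains.
- Letting the imputed Week 24 value enter the sum: the 12-letter example becomes −72 + 16 × (−12) = −264, the completer's value, provided that the imputed value matches the course. A participant with only a baseline value would still get 12c of 22c, or 54.5%, on the sustained course. This is why the intermediate visits should be imputed too.

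**The case against.** The strongest reply is that SAP 3.2.3 only defines the endpoint, and missing data belong to 4.10.1.2. The quantity is labelled as spanning 24 weeks and the Week 24 value is imputed. If that value enters the sum, the last trapezoid closes the gap and the shrinkage largely disappears. That is a sensible reading and may be what was intended. But the formula admits visits only as available, and no rule says that imputed values count as available. Two programmers could follow the text and obtain different AUCs.

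Other parts of the reply stand. Rescued participants are not pulled to zero. A missed visit in the middle of a linear course does no harm, because the trapezoid bridges it (−144 with or without Week 12). Participants who stop the drug may stay in follow-up (Protocol 2.14.10.1). The AUCs are two of 16 secondary endpoints, and the Week 24 changes in BCVA and CST are analysed separately with explicit imputation.

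The request that withdrawn participants complete the Visit 8 assessments (SAP Appendix 6.1) helps only in part. The SAP does not say whether such an assessment enters at its actual week or as Week 24.

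A reader might infer that any early leaver gets an AUC near zero whatever the course. The figures do not support this. It fits exit at about Week 4, or Week 8 on a linear course. Later exits keep 25% to 82% of the full value, and a large change stays large: a CST rise of 75 µm held to Week 12 gives 10 × 75 = 750 of 1650 µm-weeks.

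**Conclusion.** The point holds as a gap between the AUC formula and the imputation rules. Applied literally, the formula understates the AUC of unrescued participants who leave early, while rescued participants are set to the worst value at each visit. For a sustained change the understatement is proportional to the time missed. For a progressive change it is larger.

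The effect on results is small: about 1% to 5% of a group mean at the planned attrition. A reader might also infer that the arms are biased against each other. The documents give no dropout by arm, so this remains conditional on unequal dropout.

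The figures assume that f(t) is change from baseline, that no imputed value enters the sum, and that the illustrative courses apply. The primary endpoint is not touched.

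**What to change.** Replace the condition on availability in SAP 3.2.3 with a rule that the AUC always spans Weeks 0 to 24. Compute it within each of the 100 imputed data sets, after missing scheduled visits have been imputed under the MAR or composite rule that applies. Week 24 is the minimum, and all of Weeks 4 to 24 is better. Analyse each data set and combine the results with MIANALYZE. State that f(t) is change from baseline, that the same formula applies to CST, and at which week an early-withdrawal assessment enters.

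The result may be divided by 24 to give an average change in letters or microns. That is a constant rescaling for ease of reading. Division by weeks observed should not be used as the correction.

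The cost is a short SAP edit and modest extra programming, because the imputation model must be extended to the intermediate visits. No additional data are needed.
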